2. The proportion of residents in a facility whose last observed advance directive status during their observation period was DNR, DNH, DNI or feeding restrictions
 - i. The proportion of short-stay residents in a facility whose last observed advance directive status during their 100-day observation period was DNR, DNH, DNI or feeding restrictions
 - ii. The proportion of long-stay target residents in a facility whose last observed advance directive status during their 12-month observation period was DNR, DNH, DNI or feeding restrictions
 - iii. The proportion of long-stay non-target residents in a facility whose last observed advance directive status during their 12-month observation period was DNR, DNH, DNI or feeding restrictions
3. Among participants who are full code when they become part of the study (on admission to a NH), the average time to switching from full code to DNR, DNH, DNI or feeding restrictions during a 12-month observation period.

C. Burdensome interventions

1. For Aim 2.3, burdensome interventions will include: new feeding tube insertions (i.e., did not have a feeding tube at start of observation period), parenteral therapy (for hydration or medication delivery), intubation, or ICU care). The outcome will be analyzed as the proportion of long-stay target cohort residents that had any burdensome intervention during the 12-month observation period.

D. Hospice:

1. In the long-stay target cohort, the proportion of residents with any Medicare hospice claim in the 12-month observation period.
2. In the non-target long-stay cohort, the proportion of residents with any Medicare hospice claim in the 12-month observation period.
3. In the short-stay cohort without advanced comorbid conditions, the proportion of residents with any Medicare hospice claim in the 100-day observation period.
4. In the short-stay cohort with advanced comorbid conditions, the proportion of residents with any Medicare hospice claim in the 100-day observation period. For both long-stay and short-stay cohorts, residents on hospice at the start of the observation period will be excluded.

E. Medicare Advance Care Planning Billing

1. In long-stay target cohort, the proportion of residents with any Medicare ACP billing code in the 12-month observation period.
2. In non-target long-stay cohort, the proportion of residents with any Medicare ACP billing code in the 12-month observation period.

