4. SELECTION AND ENROLLMENT OF PARTICIPANTS

4.1. Facility Inclusion Criteria

Facility eligibility criteria include:

Matched facility ID on Brown University's list of all Medicare/Medicaid-certified nursing facilities in the U.S.

Serve both short and long-stay patients

Have >50 beds

Have an EMR system

Have at least 20 admissions and 20 annual Minimum Data Set (MDS) assessments (regardless of whether patients were discharged alive)

We anticipated that a total of approximately 360 (297 Genesis HealthCare / 63 PruittHealth) facilities would be eligible for random assignment.

4.2. Patient Inclusion Criteria:

As the ACP video intervention will be implemented facility-wide, all patients in eligible NHs during the 24-month implementation period are eligible. There are no exclusions based on age, gender, race, ethnicity, or clinical features.

Although the ACP intervention will be implemented facility-wide, its effectiveness will be examined among targeted NH sub-populations for Aims 2, 3, and 4. Target populations for these Aims include patients ≥ 65 in the NHs during the 24-month implementation period who meet the following eligibility definitions based on MDS assessments. For all three aims, residents will be eligible for the target sub-populations if they meet these criteria either at the start (prevalent cases) or during (incident cases) the 24-month implementation phase. Incident cases include new admissions and long-stay residents who "convert" over the implementation phase by meeting eligibility criteria based upon changes in their repeated MDS assessments.

Aim 2: Patients ≥ 65 who are in nursing home ≥ 90 days (long-stay) who have EITHER of the following two conditions:

1. *Advanced Dementia:* must have all three criteria: a, b, and c
 - a. Alzheimer's disease or other dementia
 - b. Advanced cognitive impairment*
 - c. Extensive or total assistance needed for eating and transferring

*Advanced cognitive impairment is defined as a score of 3 or 4 on the Cognitive Function Scale based on variables from the MDS Version 3.0^{119, 120}

2. *Advanced COPD/CHF:* must have all three criteria: a, b, and c
 - a. CHF/COPD
 - b. Shortness of breath sitting or lying flat
 - c. Extensive or total assistance walking in room, transferring, walking in corridor, locomotion on/off unit, or dressing.

Aim 3: Patients ≥ 65 who are in nursing home < 90 days (short-stay) who have advanced dementia OR advanced CHF/COPD as defined above.

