6.3 Data Elements

Data elements and sources are described below and in Table 2.

6.3.1. Facility-level data: Facility-level data are needed for facility recruitment, randomization, and descriptive purposes. Organizational data from OSCAR include: number of beds, for-profit status, and NH chain. Aggregated MDS data at Brown University provide information case-mix (% long-stay and post-acute care patients). MDS data are also used to calculate the hospitalization rate of each facility by estimating the number of patient days at risk of hospitalization from the nursing home and counting the number of actual hospital transfers to hospital per unit time. It is these hospital specific rates from the prior year which will be used to undertake the stratified randomization scheme (*see Section 4.4.2*). Medicare claims available at Brown University will be used to determine the facilities' hospitalization rates for the subset of patients with Medicare fee for service.

| Table 2: Data Element and Sources | | | | | |
|--|---|---------------|------------|-----------------|--------------|
| Data Element | Purpose | SOURCE | | | |
| | | EMR | MDS | Medicare | OSCAR |
| Facility-Level | | | | | |
| Organization | recruitment | | | | X |
| Case-mix | recruitment | | X | | |
| Prior Hospitalization rate | randomization | | X | | |
| | | | | | |
| Patient-Level | | | | | |
| Demographic | covariate | X | X | | |
| Long vs. short-stay | Cohort definition | | X | | |
| Functional status | target sub-population identification, covariate | | X | | |
| Cognitive status | target sub-population identification, covariate | | X | | |
| Medical condition | target sub-population identification, covariate | X | X | | |
| Insurance | covariate | | | X | |
| Advance directives | 2° outcome | X | | | |
| Health services use | 1° and 2° outcome | X | X | X | |
| Burdensome interventions | 2° outcome | X | X | X | |
| Death | description, competing risk | | X | X | |
| Intervention implementation | monitoring fidelity | X | | | |

6.3.2. Patient-level data:

6.3.2.a. Cohort description, identification of target sub-groups, and other independent variables

Demographic data: From MDS: Age, gender, race, ethnicity, religion, primary language, marital status, and length of NH stay.

Long-stay or new admission to post-acute care: From MDS.

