9. STATISTICAL CONSIDERATIONS

9.1. General Design Issues

PROVEN is pragmatic cluster RCT of an ACP Video Program intervention for NH patients cared for in two NH health care systems: Genesis HealthCare and PruittHealth. Rationale for this choice of study design is provided in Section 2.6. The intervention will be implemented facility-wide; thus, all patients in the NHs during the 24-month implementation period comprise the study population. However, the analytic plan focuses on the effect of the ACP Video Program vs. control in the following targeted patient sub-groups:

- Long-stay residents (≥ 90 days) with advanced dementia or advanced CHF/COPD (Aim 2)
- Short-stay patients (< 90 days) with advanced dementia or advanced CHF/COPD (Aim 3)
- Long and short-stay patients without these advanced illnesses (Aim 4).

The primary trial outcome is hospital transfers (number of hospital transfers/person-days alive based on Medicare claims data), which include admissions, emergency department visits, and observation stays over a 12-month follow-up period among Medicare fee-for-service long-stay residents with advanced dementia or advanced CHF/COPD. The primary hypothesis is that the rate of hospital transfers will be lower in the intervention group.

Secondary outcomes include hospital transfer rates in the sub-groups examined in Aims 3 and 4, and the following outcomes for all sub-groups in Aims 2, 3 and 4: advance directives, burdensome treatments, hospice use, and Medicare ACP billing codes.

Each long-stay resident will be followed for up to 12 months starting from the date they are first identified as meeting our target cohort definition during the 24-month intervention period and short-stay patients will be followed for 100 days from their NH admission date. The analytic approach to Aims 2, 3, and 4 are similar. Analyses begin with descriptions of all major variables using frequencies and means/medians with SDs/interquartile ranges, as appropriate. Outcomes will be compared between the control and intervention arms using a zero-inflated Poisson model

with random effects to account for clustering at the NH level. While we do not anticipate an effect on mortality, analyses will also examine the effects on mortality. Primary analyses will follow the intention to treat principle and will adjust for minor imbalances in patient characteristics, as needed.

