9.5. Data Analyses

Aim 1: To implement all aspects of a pragmatic cluster RCT: Assessment of Aim 1 will largely be experiential and based on meeting planned recruitment milestones. We will assess the implementation of the ACP Video Program by examining data from the new Video Status Report

User Defined Assessment record created in the EMR that documents the videos offered. Descriptive statistics will be generated describing the proportion of the general NH population and targeted sub-populations exposed to the video, which videos they saw, who saw them (patient and/or family members), who showed the videos (nurse, physician, social worker), and the timing of exposure (i.e., relative to admission, discharge care planning meetings).

Aim 2 To evaluate the effectiveness of the ACP intervention among long-stay NH residents with advanced comorbid conditions: The sample includes long-stay residents with advanced dementia and advanced CHF/COPD. The primary trial outcome is the hospital transfer rate (number transfers/person-days alive based on Medicare claims data), which include admissions, emergency department visits, and observation stays) over a 12-month follow-up period among Medicare fee-for-service) in this cohort. Secondary outcomes include: advance directives (DNR, DNH, DNI, no tube-feeding), burdensome treatments (new feeding tube insertion, intubation, parenteral therapy, ICU care), hospice admission, and Medicare ACP billing codes. All outcomes will be 12-month incidence measures starting from the date residents are first identified as meeting the criteria for definitions of having advanced dementia or CHF/COPD during the 24-month intervention period. While we do not anticipate the ACP intervention to affect mortality,³¹ our analyses will account for censoring during the 12-month observation period. We will formally test for a mortality differential between intervention and controls arms using a logistic regression random effects model, where clustering is performed by facility.

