Using current MDS data from CMS, we observe that the distribution of the primary outcome, hospital transfers, is over-dispersed with many of the patients having no hospital transfer over the 12-month follow up period. In addition, we also observed that hospital transfer rates vary across facilities, even after adjusting for underlying patient risk. To account for these phenomena, we will utilize a zero-inflated Poisson distribution with facility random effects to test and estimate the effects of the ACP intervention. Zero-inflated Poisson models have been used in other public health settings.^{128, 129} Formally, let Y_{ij} be the number of hospital transfers for person i in facility j , N_{ij} is the number of person days alive for person i in facility j , and T_j is a treatment indicator that is equal to one if facility j is in the intervention group. Then where β_1 is the conditional increase in the log hospital transfer rate in facilities that receive treatment vs. those that do not, and α_1 is the conditional log odds ratio for being hospitalized vs. never being hospitalized in the intervention vs. the control arm. When both α_1 and β_1 are smaller than 0, the ACP video is effective in reducing the proportion of patients hospitalized and the number of times hospitalized. Using this model we will estimate the marginal average hospital transfer rate in each arm and calculate the difference between the two arms. We will use a two sided test to examine if the marginal average difference is significantly different than zero, and we will calculate the corresponding interval estimate. As a secondary analysis, we will use the likelihood ratio test to compare the null hypothesis, $H_0 : \alpha_1 = \beta_1 = 0$, to the alternative hypothesis $H_1 : \alpha_1 \neq 0$ or $\beta_1 \neq 0$.¹³⁰ Confidence intervals for α_1 and β_1 can be obtained by inverting the likelihood ratio test.¹³² This analysis will enable us to provide additional details as to whether the effectiveness of the intervention is to reduce the likelihood of one hospital transfer or the number of hospital transfers if transferred at least once.

The secondary outcomes are binary. Commonly used methods applied to the analysis of clustered RCT with binary outcomes are GEE and multilevel models.¹³¹ The former method provides a population “average” effect, while the latter results in a conditional cluster effect. For continuous Gaussian data, interpretation of the treatment coefficient

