$$\begin{aligned}
 p(Y_{ij} = 0) &= \phi_{ij} + (1 - \phi_{ij}) \exp^{-\theta_{ij}} \\
 P(Y_{ij} = y) &= (1 - \phi_{ij}) \frac{\exp^{-\theta_{ij}} \theta_{ij}^y}{y!} \quad y = 1, 2, \dots \\
 \text{logit}(\phi_{ij}) &= \alpha_0 + \alpha_1 T_j + u_j \quad u_j \sim N(0, \sigma_u^2) \\
 \text{log}(\theta_{ij}) &= \beta_0 + \beta_1 T_j + \log(N_{ij}) + v_j \quad v_j \sim N(0, \sigma_v^2)
 \end{aligned}$$

is the same in conditional and marginal models; however, with binary data, the treatment coefficient from a marginal model is smaller than that from a conditional model and has a different interpretation.¹³² For binary outcomes, Bellamy et al¹³³ have shown that with few clusters GEE results were more likely to reject the null hypothesis, while conditional models resulted in more conservative estimates. Austin concluded that the power of GEE and multilevel models are very similar for studies, like ours, that include more than 30 clusters (facilities) with either variable or equal cluster size.¹³⁴ To estimate the effect of ACP on secondary outcomes we will use random effects logistic model. Formally, let S_{ij} one of the secondary outcomes for person i in facility j , and T_j is a treatment indicator that is equal to one if facility j is in the treated arm.

$$\begin{aligned}
 S_{ij} &\sim \text{Ber}(p_{ij}) \\
 \text{logit}(p_{ij}) &= \gamma_0 + \gamma_1 T_j + \zeta_j \\
 \zeta_j &\sim N(0, \sigma_\zeta^2)
 \end{aligned}$$

where γ_1 is the conditional log odds ratio for observing the secondary outcome in the treatment arm vs. the control arm. When γ_1 is smaller than 0, ACP is effective. As for the primary outcome we will use the likelihood ratio test the null hypothesis $H_0 : \gamma_1 = 0$, and by inverting this test we will obtain the corresponding confidence interval.

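### The B.3 time-to-switching measure is undefined for non-switchers and decedents, does not fit the planned logistic model, and its start and window do not match the stated follow-up (minor)

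*Combined protocol and SAP*

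**What the plan says.** Item B.3 of the cohort and outcome specifications (Section 1) takes its population as "Among participants who are full code when they become part of the study (on admission to a NH" and measures "the average time to switching from full code to DNR, DNH, DNI or feeding restrictions during a 12-month observation period". Unlike B.2, which splits its proportions into short-stay, long-stay target and long-stay non-target residents, B.3 names no cohort.

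Section 9.1 has each long-stay resident "followed for up to 12 months starting from the date they are first identified as meeting our target cohort definition", and follows short-stay patients for 100 days from admission. Section 4.2 admits target patients who qualify "either at the start (prevalent cases) or during (incident cases) the 24-month implementation phase".

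On analysis, Section 9.5 states: "The secondary outcomes are binary". It then says: "To estimate the effect of ACP on secondary outcomes we will use random effects logistic model". The only other outcome model for the main analyses is a zero-inflated Poisson model for counts of transfers.

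On incomplete follow-up there are two general remarks. Section 9.5 (Aim 2) says "our analyses will account for censoring during the 12-month observation period", and Table 2 in Section 6.3 gives the purpose of the death variable as "description, competing risk". Neither is followed by an estimator or a rule.

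Item B.1 limits all directive analyses to Genesis facilities where more than 75% of patients have any advance directive. It gives data reliability as the reason and no date or period for the percentage.

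**The concern.** The stated measure and the stated model conflict, so an analyst cannot carry out B.3 as written. Several calculations could claim to implement it: average over switchers only, stop the clock at death, or score non-switchers and decedents at 12 months. They estimate different things. The most literal one, switchers only, conditions on an event that happens after randomization and that the program is meant to cause. It therefore compares two differently selected groups. A program that persuades more people to switch, but later, would lengthen the average and look harmful. Because the plan does not choose, the choice could be made after the data are seen.

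B.3 is also the only directive item restricted to people who start as full code, so it is a natural place to look for change in status.

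**Working it through.** The plan gives no rate, event count or power figure for B.3. Its sample size concerns the primary outcome only, so there is no figure to reproduce.

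**Step 1. Start and window side by side.**

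| Source | Group | Start | Window |
|---|---|---|---|
| Section 1, B.3 | full-code entrants, cohort not named | NH admission | 12 months |
| Section 9.1 | long-stay target | date criteria first met | up to 12 months |
| Section 9.1 | short-stay | NH admission | 100 days |
| Section 1, B.2.iii | long-stay non-target | none given; Section 9.1 ties the start to the target definition | 12 months |

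Long-stay means at least 90 days in the home (Section 4.2), so long-stay follow-up cannot begin at admission. For prevalent residents, admission precedes study entry. B.3 shares its window with one cohort and its start with the other, but both with neither.

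**Step 2. How far the unstated choice moves the answer.**

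Inputs:
- Death hazard μ, from Section 9.5 (Aim 3), where 30% (CHF/COPD) and nearly 50% (dementia) of post-acute target patients died within 6 months. μ = −ln(0.7)/0.5 = 0.71 and −ln(0.5)/0.5 = 1.39 per year, extrapolated to 12 months.
- Assumed: switching hazard λ = 0.2 (control) and 0.4 (intervention) per year, constant; 500 full-code entrants per arm; no clustering.

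Formulas, with a = λ + μ and S = exp(−a) at one year:
- 12-month incidence P = (λ/a)(1 − S)
- mean among switchers M = 12[1/a − S/(1 − S)] months
- clock stopped at death: 12(1 − S)/a months
- non-switchers and deaths scored at 12: P·M + (1 − P)·12 months

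At μ = 0.71, control: a = 0.913, S = 0.401, P = (0.2/0.913)(0.599) = 13.1%, M = 5.10. Intervention: a = 1.113, S = 0.328, P = (0.4/1.113)(0.672) = 24.1%, M = 4.91.

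Incidence: z = 0.110/√(0.131·0.869/500 + 0.241·0.759/500) = 0.110/0.0244 = 4.5.

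Switchers only: SDs are 3.39 and 3.36 months, with 66 and 121 switchers. z = 0.19/√(3.39²/66 + 3.36²/121) = 0.19/0.52 = 0.4.

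| Measure | μ = 0.71 | z | μ = 1.39 | z |
|---|---|---|---|---|
| 12-month incidence | 13.1% vs 24.1% | 4.5 | 10.0% vs 18.6% | 3.9 |
| Average, switchers only (months) | 5.10 vs 4.91 | 0.4 | 4.48 vs 4.30 | 0.3 |
| Average, clock stops at death | 7.87 vs 7.24 | 2.3 | 6.02 vs 5.59 | 1.6 |
| Average, others scored at 12 | 11.10 vs 10.29 | 4.2 | 11.25 vs 10.57 | 3.7 |

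An assumed design effect of 1.2 to 2.0 takes the 4.5 to 4.5/√1.2 = 4.1 or 4.5/√2.0 = 3.2.

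**Step 3. The sign depends on when the extra switches occur** (μ = 0.71, hazards assumed).

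- Late effect. Both arms 0.40 per year in months 0–3, then 0.133; the intervention rises to 0.533 from month 6. Incidence goes from 14.3% to 23.2% (z 3.6). The switchers-only average lengthens from 3.6 to 5.5 months (z −3.7). The version scored at 12 months gives z of about 1.5.
- Early effect. Control 0.2 throughout; intervention 1.0 in months 0–3, then 0.2. Incidence goes from 13.1% to 27.4%, and the average falls from 5.1 to 2.8 months (z 4.7).

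The reversal can be checked by hand. Suppose 20% of controls switch, at 1.5 months on average, and the program adds 15% who switch at 7.5 months on average. The switchers-only mean is 1.5 in control and (0.20·1.5 + 0.15·7.5)/0.35 = 4.1 in intervention. Scoring everyone else at 12 gives 0.20·1.5 + 0.80·12 = 9.9 against 0.35·4.07 + 0.65·12 = 9.2, the opposite direction.

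**Step 4. The horizon matters too.** With the constant hazards of Step 2, the difference in incidence at 100 days is 4.8% to 9.4% (4.6 points) at μ = 0.71, against 11.0 points at 12 months. At μ = 1.39 it is 4.4% to 8.7% (4.2 points from unrounded values), against 8.6 points.

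**The case against.** It can be said in the plan's favour that B.3 does state a start and a window. The bracketed phrase about admission may limit it to new admissions, for whom study entry and admission coincide; the difficulty with prevalent residents then disappears. This stands in part. A reader might infer that B.3 has no clock at all, and that is wrong. What remains is that a 12-month window from admission is not the follow-up Section 9.1 gives either cohort.

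The plan also says that Aim 2 analyses will account for censoring and labels death a competing risk. A switchers-only mean does neither, so the most damaging calculation runs against the plan's evident intent. That is a fair limit, and it would be wrong to say that the plan ignores death. But intent without an estimator does not rule the calculation out, and the remaining versions still differ widely (z 2.3 against 4.2 in the first scenario).

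The reversal needs a constructed late effect, and an early effect gives the expected direction. The mortality inputs come from post-acute patients, whom the plan follows for 100 days only. Both objections are correct. The figures illustrate and do not predict.

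Sections 1, 9.4.2 and 9.5 describe the short-stay directive window variously as 100 days, the admission and the nursing home stay. A reader might see a further contradiction. Since a short stay is under 90 days and directives come only from the home's EMR, these cover nearly the same data, so this is mostly wording.

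**Conclusion.** The point holds as a minor one. B.3's measure has no value for non-switchers and decedents, no model in the plan analyses a time, and its start and window need reconciling with Section 9.1. The conflict between an average time and a binary-outcome model rests on the text alone. The size of the consequence rests on assumed switching hazards, extrapolated mortality, 500 entrants per arm and no clustering; under those, one reading hides a clear effect (z 0.4 against 4.5) and can reverse it.

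Two stronger conclusions are not supported. First, a reader might infer that the directive hypotheses cannot be tested. H2a, H3a and H4a are stated as proportions, B.2 supplies proportions, and the logistic model fits them. B.3 is a supplementary measure tied to no numbered hypothesis, and the primary outcome and sample size are untouched. Second, a reader might infer that the >75% screen biases the directive results. The documents do not say when the percentage is measured. A trial-period calculation could select facilities on something the program may change, but there is no bias if recording does not differ by arm, and the documents give no inputs from which to size one.

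**What to change.** 1. Replace the average with the cumulative incidence of a first limiting order by the cohort's horizon, among all full-code entrants. Treat death as a competing event, and live discharge as another because directives come from the nursing home EMR. Non-switchers and decedents then stay in the denominator.
2. With complete follow-up to the horizon this is a simple proportion, and the planned facility random-effects logistic model can analyse it. If follow-up is incomplete, name one competing-risk method that allows for clustering by facility.
3. Name the cohorts and state start and horizon for each, consistent with Section 9.1: cohort identification and 12 months for long-stay target residents, admission and 100 days for short-stay patients. Add a start date for long-stay non-target residents, who have none. Use one wording for the short-stay directive window.
4. Separately, define the >75% screen from pre-implementation data or, failing that, the earliest available data. Compute it identically in both arms and fix the facility list blind to outcome.

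The cost is SAP wording, possibly one added model, and one run of the facility screen. The screen may leave fewer facilities in the directive analyses. Section 6.2 describes EMR transfers during the full trial, so pre-implementation extracts may not exist; the earliest extracts could then include some exposure in first-wave facilities.
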